#### 11.1.1 Definitions

Evaluable for Target Disease response. Only those participants who have measurable disease present at baseline, have received at least one cycle of therapy, and have had their disease re-evaluated will be considered evaluable for target disease response. These participants will have their response classified according to the definitions stated below. (Note: Participants who exhibit objective disease progression prior to the end of cycle 1 will also be considered evaluable.)

Evaluable Non-Target Disease Response. Participants who have lesions present at baseline that are evaluable but do not meet the definitions of measurable disease, have received at least one cycle of therapy, and have had their disease re-evaluated will be considered evaluable for non-target disease. The response assessment is based on the presence, absence, or unequivocal progression of the lesions.

#### 11.1.2 Disease Parameters

Measurable disease. Measurable lesions are defined as those that can be accurately measured in at least one dimension (longest diameter to be recorded) as  $\geq 20$  mm by chest x-ray or  $\geq 10$  mm with CT scan, MRI, or calipers by clinical exam. All tumor measurements must be recorded in millimeters (or decimal fractions of centimeters).

Note: Tumor lesions that are situated in a previously irradiated area might or might not be considered measurable. *If the investigator thinks it appropriate to include them, the conditions under which such lesions should be considered must be defined in the protocol.*

Malignant lymph nodes. To be considered pathologically enlarged and measurable, a lymph node must be  $\geq 15$  mm in short axis when assessed by CT scan (CT scan slice thickness recommended to be no greater than 5 mm). At baseline and in follow-up, only the short axis will be measured and followed.

**Non-measurable disease.** All other lesions (or sites of disease), including small lesions (longest diameter <10 mm or pathological lymph nodes with  $\geq 10$  to <15 mm short axis), are considered non-measurable disease. Bone lesions, leptomeningeal disease, ascites, pleural/pericardial effusions, lymphangitis cutis/pulmonitis, inflammatory breast disease, abdominal masses (not followed by CT or MRI), and cystic lesions are all considered non-measurable.

Note: Cystic lesions that meet the criteria for radiographically defined simple cysts should not be considered as malignant lesions (neither measurable nor non-measurable) since they are, by definition, simple cysts.

‘Cystic lesions’ thought to represent cystic metastases can be considered as measurable lesions, if they meet the definition of measurability described above. However, if non-cystic lesions are present in the same participant, these are preferred for selection as target lesions.

**Target lesions.** All measurable lesions up to a maximum of 2 lesions per organ and 5 lesions in total, representative of all involved organs, should be identified as **target lesions** and recorded and measured at baseline. Target lesions should be selected on the basis of their size (lesions with the longest diameter), be representative of all involved organs, but in addition should be those that lend themselves to reproducible repeated measurements. It may be the case that, on occasion, the largest lesion does not lend itself to reproducible measurement in which circumstance the next largest lesion which can be measured reproducibly should be selected. A sum of the diameters (longest for non-nodal lesions, short axis for nodal lesions) for all target lesions will be calculated and reported as the baseline sum diameters. If lymph nodes are to be included in the sum, then only the short axis is added into the sum. The baseline sum diameters will be used as reference to further characterize any objective tumor regression in the measurable dimension of the disease.

**Non-target lesions.** All other lesions (or sites of disease) including any measurable lesions over and above the 5 target lesions should be identified as **non-target lesions** and should also be recorded at baseline. Measurements of these lesions are not required, but the presence, absence, or in rare cases unequivocal progression of each should be noted throughout follow up.

#### 11.1.3 Methods for Evaluation of Disease

All measurements should be taken and recorded in metric notation using a ruler, calipers, or a digital measurement tool. All baseline evaluations should be performed as closely as possible to the beginning of treatment and never more than 4 weeks before the beginning of the treatment.

The same method of assessment and the same technique should be used to characterize each identified and reported lesion at baseline and during follow-up. Imaging-based

evaluation is preferred to evaluation by clinical examination unless the lesion(s) being followed cannot be imaged but are assessable by clinical exam.

Clinical lesions. Clinical lesions will only be considered measurable when they are superficial (*e.g.*, skin nodules and palpable lymph nodes) and  $\geq 10$  mm in diameter as assessed using calipers (*e.g.*, skin nodules). In the case of skin lesions, documentation by color photography, including a ruler to estimate the size of the lesion, is recommended.

Chest x-ray. Lesions on chest x-ray are acceptable as measurable lesions when they are clearly defined and surrounded by aerated lung; however, CT is preferable.

Conventional CT and MRI. This guideline has defined measurability of lesions on CT scan based on the assumption that CT thickness is 5mm or less. If CT scans have slice thickness greater than 5 mm, the minimum size of a measurable lesion should be twice the slice thickness. MRI is also acceptable in certain situations (*e.g.* for body scans).

Use of MRI remains a complex issue. MRI has excellent contrast, spatial, and temporal resolution; however, there are many image acquisition variables involved in MRI, which greatly impact image quality, lesion conspicuity, and measurement. Furthermore, the availability of MRI is variable globally. As with CT, if an MRI is performed, the technical specifications of the scanning sequences used should be optimized for the evaluation of the type and site of disease. Furthermore, as with CT, the modality used at follow-up should be the same as was used at baseline and the lesions should be measured/assessed on the same pulse sequence. It is beyond the scope of the RECIST guidelines to prescribe specific MRI pulse sequence parameters for all scanners, body parts, and diseases. Ideally, the same type of scanner should be used and the image acquisition protocol should be followed as closely as possible to prior scans. Body scans should be performed with breath-hold scanning techniques, if possible.

FDG-PET. While FDG-PET response assessments need additional study, it is sometimes reasonable to incorporate the use of FDG-PET scanning to complement CT scanning in assessment of progression (particularly possible 'new' disease). New lesions on the basis of FDG-PET imaging can be identified according to the following algorithm:

- (a) Negative FDG-PET at baseline, with a positive FDG-PET at follow-up is a sign of PD based on a new lesion.
- (b) No FDG-PET at baseline and a positive FDG-PET at follow-up: If the positive FDG-PET at follow-up corresponds to a new site of disease confirmed by CT, this is PD. If the positive FDG-PET at follow-up is not confirmed as a new site of disease on CT, additional follow-up CT scans are needed to determine if there is truly progression occurring at that site (if so, the date of PD will be the date of the initial abnormal FDG-PET scan). If the positive FDG-PET at follow-up corresponds to a pre-existing site of disease on CT that is not progressing on the basis of the anatomic images, this is not PD.
- (c) FDG-PET may be used to upgrade a response to a CR in a manner similar to a biopsy in cases where a residual radiographic abnormality is thought to represent fibrosis or scarring. The use of FDG-PET in this circumstance should be

prospectively described in the protocol and supported by disease-specific medical literature for the indication. However, it must be acknowledged that both approaches may lead to false positive CR due to limitations of FDG-PET and biopsy resolution/sensitivity.

Note: A 'positive' FDG-PET scan lesion means one which is FDG avid with an uptake greater than twice that of the surrounding tissue on the attenuation corrected image.

PET-CT. At present, the low dose or attenuation correction CT portion of a combined PET-CT is not always of optimal diagnostic CT quality for use with RECIST measurements. However, if the site can document that the CT performed as part of a PET-CT is of identical diagnostic quality to a diagnostic CT (with IV and oral contrast), then the CT portion of the PET-CT can be used for RECIST measurements and can be used interchangeably with conventional CT in accurately measuring cancer lesions over time. Note, however, that the PET portion of the CT introduces additional data which may bias an investigator if it is not routinely or serially performed.

Ultrasound. Ultrasound is not useful in assessment of lesion size and should not be used as a method of measurement. Ultrasound examinations cannot be reproduced in their entirety for independent review at a later date and, because they are operator dependent, it cannot be guaranteed that the same technique and measurements will be taken from one assessment to the next. If new lesions are identified by ultrasound in the course of the study, confirmation by CT or MRI is advised. If there is concern about radiation exposure from CT, MRI may be used instead of CT in selected instances.

Endoscopy, Laparoscopy. The utilization of these techniques for objective tumor evaluation is not advised. However, such techniques may be useful to confirm complete pathological response when biopsies are obtained or to determine relapse in trials where recurrence following complete response (CR) or surgical resection is an endpoint.

Cytology, Histology. These techniques can be used to differentiate between partial responses (PR) and complete responses (CR) in rare cases (e.g., residual lesions in tumor types, such as germ cell tumors, where known residual benign tumors can remain).

The cytological confirmation of the neoplastic origin of any effusion that appears or worsens during treatment when the measurable tumor has met criteria for response or stable disease is mandatory to differentiate between response or stable disease (an effusion may be a side effect of the treatment) and progressive disease.

#### 11.1.3.1 Evaluation of Target Lesions

Complete Response (CR): Disappearance of all target lesions. Any pathological lymph nodes (whether target or non-target) must have reduction in short axis to <10 mm.

Partial Response (PR): At least a 30% decrease in the sum of the diameters of target lesions, taking as reference the baseline sum diameters.

Progressive Disease (PD): At least a 20% increase in the sum of the diameters of target lesions, taking as reference the smallest sum on study (this includes the baseline sum if that is the smallest on study). In addition to the relative increase of 20%, the sum must also demonstrate an absolute increase of at least 5 mm. (Note: the appearance of one or more new lesions is also considered progressions).

Stable Disease (SD): Neither sufficient shrinkage to qualify for PR nor sufficient increase to qualify for PD, taking as reference the smallest sum diameters while on study.

#### 11.1.3.2 Evaluation of Non-Target Lesions

Complete Response (CR): Disappearance of all non-target lesions and normalization of tumor marker level. All lymph nodes must be non-pathological in size (<10 mm short axis).

Note: If tumor markers are initially above the upper normal limit, they must normalize for a patient to be considered in complete clinical response.

Non-CR/Non-PD: Persistence of one or more non-target lesion(s) and/or maintenance of tumor marker level above the normal limits.

Progressive Disease (PD): Appearance of one or more new lesions and/or *unequivocal progression* of existing non-target lesions. *Unequivocal progression* should not normally trump target lesion status. It must be representative of overall disease status change, not a single lesion increase.

Although a clear progression of “non-target” lesions only is exceptional, the opinion of the treating physician should prevail in such circumstances, and the progression status should be confirmed at a later time by the review panel (or Principal Investigator).

#### 11.1.3.3 Evaluation of New Lesions

The finding of a new lesion should be unequivocal (i.e. not due to difference in scanning technique, imaging modality, or findings thought to represent something other than tumor (for example, some ‘new’ bone lesions may be simply healing or flare of pre-existing lesions). However, a lesion identified on a follow-up scan in an anatomical location that was not scanned at baseline is considered new and will

indicate PD. If a new lesion is equivocal (because of small size etc.), follow-up evaluation will clarify if it truly represents new disease and if PD is confirmed, progression should be declared using the date of the initial scan on which the lesion was discovered.

#### 11.1.3.4 Evaluation of Best Overall Response

The best overall response is the best response recorded from the start of the treatment until disease progression/recurrence (taking as reference for progressive disease the smallest measurements recorded since the treatment started). The patient's best response assignment will depend on the achievement of both measurement and confirmation criteria.

#### For Participants with Measurable Disease (*i.e.*, Target Disease)

Target Lesions	Non-Target Lesions	New Lesions	Overall Response	Best Overall Response when Confirmation is Required*
CR	CR	No	CR	$\geq 4$ wks Confirmation**
CR	Non-CR/Non-PD	No	PR	$\geq 4$ wks Confirmation**
CR	Not evaluated	No	PR	
PR	Non-CR/Non-PD/not evaluated	No	PR	
SD	Non-CR/Non-PD/not evaluated	No	SD	Documented at least once $\geq 4$ wks from baseline**
PD	Any	Yes or No	PD	no prior SD, PR or CR
Any	PD***	Yes or No	PD	
Any	Any	Yes	PD	

\* See RECIST 1.1 manuscript for further details on what is evidence of a new lesion.  
 \*\* Only for non-randomized trials with response as primary endpoint.  
 \*\*\* In exceptional circumstances, unequivocal progression in non-target lesions may be accepted as disease progression.

Note: Participants with a global deterioration of health status requiring discontinuation of treatment without objective evidence of disease progression at that time should be reported as “*symptomatic deterioration*.” Every effort should be made to document the objective progression even after discontinuation of treatment.

#### For Participants with Non-Measurable Disease (*i.e.*, Non-Target Disease)

Non-Target Lesions	New Lesions	Overall Response
CR	No	CR
Non-CR/non-PD	No	Non-CR/non-PD*
Not all evaluated	No	not evaluated

Unequivocal PD	Yes or No	PD
Any	Yes	PD
* 'Non-CR/non-PD' is preferred over 'stable disease' for non-target disease since SD is increasingly used as an endpoint for assessment of efficacy in some trials so to assign this category when no lesions can be measured is not advised		

#### 11.1.4 Duration of Response

Duration of overall response: The duration of overall response is measured from the time measurement criteria are met for CR or PR (whichever is first recorded) until the first date that recurrent or progressive disease is objectively documented (taking as reference for progressive disease the smallest measurements recorded since the treatment started, or death due to any cause. Participants without events reported are censored at the last disease evaluation).

Duration of overall complete response: The duration of overall CR is measured from the time measurement criteria are first met for CR until the first date that progressive disease is objectively documented, or death due to any cause. Participants without events reported are censored at the last disease evaluation.

Duration of stable disease: Stable disease is measured from the start of the treatment until the criteria for progression are met, taking as reference the smallest measurements recorded since the treatment started, including the baseline measurements.

#### 11.1.5 Progression-Free Survival

Overall Survival: Overall Survival (OS) is defined as the time from randomization (or registration) to death due to any cause, or censored at date last known alive.

Progression-Free Survival: Progression-Free Survival (PFS) is defined as the time from randomization (or registration) to the earlier of progression or death due to any cause. Participants alive without disease progression are censored at date of last disease evaluation.

Time to Progression: Time to Progression (TTP) is defined as the time from randomization (or registration) to progression, or censored at date of last disease evaluation for those without progression reported.

## 12. DATA REPORTING / REGULATORY REQUIREMENTS

Adverse event lists, guidelines, and instructions for AE reporting can be found in Section 7.0 (Adverse Events: List and Reporting Requirements).

### 12.1 Data Reporting

### **12.1.1 Method**

The Office of Data Quality (ODQ) will collect, manage, and perform quality checks on the data for this study.

### **12.1.2 Responsibility for Data Submission**

Investigative sites within DF/HCC or DF/PCC are responsible for submitting data and/or data forms to the Office of Data Quality in accordance with DF/HCC SOPs.

## **12.2 Data Safety Monitoring**

The DF/HCC Data and Safety Monitoring Committee (DSMC) will review and monitor toxicity and accrual data from this study. The committee is composed of clinical specialists with experience in oncology and who have no direct relationship with the study. Information that raises any questions about participant safety will be addressed with the Overall PI and study team.

The DSMC will review each protocol up to four times a year or more often if required to review toxicity and accrual data. Information to be provided to the committee may include: up-to-date participant accrual; current dose level information; DLT information; all grade 2 or higher unexpected adverse events that have been reported; summary of all deaths occurring with 30 days of intervention for Phase I or II protocols; for gene therapy protocols, summary of all deaths while being treated and during active follow-up; any response information; audit results, and a summary provided by the study team. Other information (e.g. scans, laboratory values) will be provided upon request.

## **13. STATISTICAL CONSIDERATIONS**

### **13.1 Study Design/Endpoints**

This is a pilot phase II clinical trial with a primary endpoint of objective response per RECIST 1.1 among patients with metastatic or unresectable angiosarcoma and EHE treated with Eribulin.

For the primary endpoint of best overall objective response with a null hypothesis of 10% and an alternative hypothesis of 35%, we would need 16 patients in a single-stage design. We will need to observe at least 4 responses out of 16 patients to accept the treatment. The power for this design is 87% using the exact binomial distribution. The operating characteristics of this design are calculated using one-sided 10% type I error.

### **13.2 Sample Size, Accrual Rate and Study Duration**

For the primary endpoint of best overall objective response with parameters as described in 13.1, a total sample size of 16 patients is needed in a single-stage design. A minimum accrual rate is

expected to be 1 subjects per two months. With a minimal accrual rate of **0.5** subjects per month, we expect the study enrollment to last approximately **32** months.

### **13.3 Interim Monitoring Plan**

Please see section 12.1 for safety monitoring by the DF/HCC DSMB. There is no other interim monitoring plan for this pilot study.

### **13.4 Analysis of Primary Endpoints**

The best overall objective response rate is defined as, the proportion of patients with complete [CR] or partial response [PR] per RECIST 1.1 among all eligible angiosarcoma and EHE patients treated with Eribulin. Disease assessment will be performed every 6 weeks for the first 8 cycles and then every 9 weeks or as clinically indicated thereafter. The two-sided 95% exact binomial confidence interval will be computed for objective response.

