### **13.5 Analysis of Secondary Endpoints**

There is at least 74% probability of observing one or more rare (8% true probability) events, and 93% probability of observing toxicities that have a true occurrence of at least 15%. With 16 treated patients, the maximum width of a 90% two-sided exact binomial confidence interval for any estimated adverse event proportion will be no wider than  $\pm 22\%$ .

Progression-free survival will also be calculated. Progression-free survival, will be defined as the duration of time from start of treatment to time of progression or death, whichever occurs first and will be estimated using the Kaplan-Meier method. The disease control rate (Complete Response, Partial Response, and Stable Disease) at 24 weeks will also be calculated using the exact binomial distribution and 95% confidence interval.

We will explore the relationship between integrated biomarkers detected by cfDNA exome sequencing, WES, RNAseq expression profiling and response to Eribulin. We will use Fisher's Exact Test to assess the relationship between each biomarker and response to eribulin assuming a best overall objective response of 35%. Biomarkers may be continuous or binary. For example, with this design, assuming tissue is available on 100% of the sample, the probability of concluding eribulin response is related to the exploratory biomarker is 82%; given the unknown true response is 70% and 4% in positive marker versus negative marker patients, respectively, assuming 50% of the population is over-expressed for the biomarker or the biomarker is continuous and split at the median. The operating characteristics of this design are calculated using a two-sided exact test with 10% type I error.

We will explore the relationship between changes in the integrated biomarkers from baseline to cycle 3 due to eribulin treatment using a paired t-test. With 16 patients, we will have 81% power to detect an effect size of 0.67 using a paired t-test with a 0.1 two-sided significance level.

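### Does a two-sided 95% interval for response conflict with a success rule set at one-sided 10%?

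*Combined protocol and SAP*

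**What the plan says.** Section 13.1 (Study Design/Endpoints) gives the hypotheses as "a null hypothesis of 10% and an alternative hypothesis of 35" per cent, and the size as "we would need 16 patients in a single-stage design". The decision rule is stated in responses: "We will need to observe at least 4 responses out of 16 patients to accept the treatment". Its properties follow: "The power for this design is 87% using the exact binomial distribution" and "The operating characteristics of this design are calculated using one-sided 10% type I error".

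Section 13.4 (Analysis of Primary Endpoints) defines the response rate and adds one inferential summary: "The two-sided 95% exact binomial confidence interval will be computed for objective response". It does not repeat the rule of four. It also does not say that the interval decides anything or must exclude 10%.

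Section 13.5 (Analysis of Secondary Endpoints) uses 95% for the disease control rate at 24 weeks. For toxicity it uses 90%, describing "the maximum width of a 90% two-sided exact binomial confidence interval for any estimated adverse event proportion".

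**The concern.** A two-sided 95% exact interval puts 2.5% in its lower tail. Asking whether its lower limit clears 10% is therefore a one-sided 2.5% test, four times stricter than the 10% limit in section 13.1. A trial that just succeeds would announce a positive result beside an interval that has not ruled out the null rate.

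The worry is that the conclusion could then be argued either way after the data are seen: success from section 13.1, or an inconclusive result from section 13.4. A reader who treated the interval as the real criterion would in effect demand five responses, which is a less powerful design than the one planned. Section 13.1 also quotes the 10% error limit and not the smaller error that the rule attains, so the strength of evidence at 4/16 is not visible on the page.

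**Working it through.** **Inputs.** From section 13.1: n = 16, null rate 10%, alternative 35%, success at 4 or more responses, one-sided limit 10%, stated power 87%. From section 13.4: two-sided 95% exact binomial interval, taken as Clopper-Pearson. The analysed denominator is assumed to be exactly 16.

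**1. Reproduce the design.** With X binomial(16, p), the chance of success is P(X ≥ 4) = 1 − P(0) − P(1) − P(2) − P(3).

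- At p = 10%: 1 − (0.1853 + 0.3294 + 0.2745 + 0.1423) = 1 − 0.9315 ≈ 0.068 (0.0684 unrounded). This is within the 10% limit.
- At p = 35%: 0.8661, which matches the stated 87%.
- The cut-off is the right one for the limit. Success at 3 or more would have error 0.2108, above 10%. Success at 5 or more would have error 0.0170 and power 0.7108.

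**2. Compare the rule with the interval.** The Clopper-Pearson limits for x responses at confidence level 1 − a are beta quantiles:

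- lower = Beta(a/2; x, n − x + 1)
- upper = Beta(1 − a/2; x + 1, n − x)

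The lower limit exceeds 10% exactly when the one-sided p-value P(X ≥ x | 10%) is below a/2. For the 95% interval a/2 = 0.025. For a two-sided 80% interval a/2 = 0.10, which is the level in section 13.1.

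| Responses | One-sided p | Rule | 95% interval | Contains 10%? |
|---|---|---|---|---|
| 2/16 | 0.4853 | not met | 1.6% to 38.4% | yes |
| 3/16 | 0.2108 | not met | 4.1% to 45.7% | yes |
| 4/16 | 0.0684 | met | 7.3% to 52.4% | yes |
| 5/16 | 0.0170 | met | 11.0% to 58.7% | no |
| 6/16 | 0.0033 | met | 15.2% to 64.6% | no |

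At 0 and 1 responses the rule also fails and the interval contains 10% (upper limits 20.6% and 30.2%). Above 6 the lower limit only rises. The sole disagreement is at 4/16, the one count whose p-value lies between 0.025 and 0.10.

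**3. How often that count occurs.**

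- P(X = 4 | 35%) = 0.1553, which is 0.1553 / 0.8661 = 17.9% of successful trials.
- P(X = 4 | 10%) = 0.0514, which is 0.0514 / 0.0684 = 75% of false positives.

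**4. The interval that would match the rule.** The two-sided 80% interval is 11.4% to 43.9% at 4/16 and 7.1% to 37.1% at 3/16, so it agrees with the rule on both sides of the cut-off. A 90% interval does not: at 4/16 it is 9.0% to 48.4%.

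**The case for a change.** The best case for a change is that 4/16 is a realistic result, that most false positives fall there, and that the plan does not say in advance how to read it. Section 13.4 neither restates the rule nor calls the interval descriptive, and section 13.5 uses other levels without linking them. One sentence would settle the order of precedence at almost no cost.

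The arithmetic behind this stands, and so does the silence. The harm does not. Section 13.1 names the criterion in plain terms, and section 13.4 only reports an estimate. Testing and estimation are separate tasks and may use different levels. The drop in power from 86.6% to 71.1%, and in error from 6.8% to 1.7%, describes a five-response rule that would have to be brought in from outside the plan.

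That 75% of false positives fall at 4/16 is a property of the count rule, and no choice of interval alters it. If anything it favours the wider interval, because a lower limit of 7.3% tells the reader how thin the evidence is at the boundary, while 11.4% conveys less of that. Replacing it with an 80% interval would also put response on a different scale from the disease control rate.

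The unprinted 6.8% is a detail. Section 13.1 can fairly be read as giving the design limit, the rule respects it, and anyone can recover the attained value from n, the cut-off and the null rate.

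**Conclusion.** The mismatch is real but limited to one of the 17 possible counts, and it is not an error. Followed as written, the plan gives a decision rule with 6.8% type I error and 86.6% power, and a valid exact interval for the response rate. At 4/16 both statements would be true together: the result passes a screening threshold at one-sided p = 0.068, and a response rate of 10% is not excluded at the stricter 2.5% level. A competent report says both.

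Stating that the count governs, adding the 80% interval, or printing the attained error would each make the text more explicit. None would alter the sample size, the rule, the error rates or the conclusion at any count. Preferring an 80% interval as the main summary is a matter of taste.

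This rests on 16 patients being analysed and on the exact interval being Clopper-Pearson. With a different denominator the boundary figures would need recalculating, but the count-based decision and the descriptive role of the interval would still be distinct.
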